#### 6.0 Definitions of Analysis Sets and Subgroups

A total of three populations will be defined including the intent-to-treat population (ITT), per-protocol (PP) population, and the safety population.

#### 6.1 Intent-to-Treat Population

The intent-to-treat (ITT) population will include all randomized subjects and will be analyzed according to their randomized treatment assignment. In the event that randomized subjects never started treatment, a modified intent-to-treat (mITT) population will be used which is defined as the ITT that received at least one dose of study product and at least one post randomization measurement. The primary efficacy analysis will be conducted on the ITT/mITT population.

#### 6.2 Per Protocol (PP) Population

The per protocol (PP) will include subjects who completed the study according to the protocol. Exclusion from the PP will occur if subject fails to meet one or more of the inclusion criteria at enrollment (section 4.2.1 of the protocol) or meets one or more of the exclusion criteria (section 4.2.2 of the protocol). Data will be excluded if the subject has other significant protocol deviations or significant non-compliance with study product. Compliance (%) will be determined by capsule counts calculated as: (the number of capsules provided – the number of capsules returned) divided by the number of expected capsules taken multiplied by 100. The expected number of capsules will be defined as the duration of treatment (end of study medication- start of study medication +1) multiplied by three. Subjects must take a minimum of 80% of expected capsules to be considered compliant. The per protocol (PP) population will be determined at a blinded data review meeting.

# 6.3 Safety Population

The safety population will be comprised of the intent-to-treat population and will include all randomized subjects. Subjects will be analyzed according to the product actually received during the study. All safety analyses will be performed on the safety population.

# 6.4 Subgroups

Subgroup analyses will be performed for the exploratory endpoint pertaining to the transcriptomic analysis of the PBMC gene expression. In order to obtain 40 subjects (~10 subjects / treatment arm) in the PBMC gene expression analysis set, samples from the first 55 subjects enrolled and randomized will be obtained and analyzed.

# 6.5 Unblinded compliance population

Blood levels for DHA and Vitamin E ( $\alpha$ -tocopheryl) will be used to confirm the accuracy of capsule counts used in the determination of the PP population. The unblinded compliance population will be defined after database lock. For each subject, the change from baseline to each follow-up time point (3 and 6 months) will be calculated following the cutoffs in Table 2. For subjects randomized to placebo, a change in DHA >26µg/mL or in Vitamin E ( $\alpha$ -tocopheryl) >18µmol/L at 6-month will be considered non-compliant. For subjects randomized to DHA EE, subjects with an increase in  $\alpha$ -tocopheryl blood level (>18µmol/L) and/or a small change in DHA level (<10 µg/mL) will be considered non-compliant. For subjects randomized to vitamin E, a significant increase in DHA blood level (>26µg/mL) and/or a small change in Vitamin E ( $\alpha$ -tocopheryl non-compliant. Finally, for subjects randomized to DHA EE + vitamin E, if neither the Vitamin E level (<7µmol/L) nor the DHA (<10 µg/mL) increases sufficiently, the subjects will be considered non-compliant.

| Observed change in Placebo: exclude if more than |    | Treated: exclude if less than |
|--|----|-------------------------------|
| DHA (µg/ml)                                      | 26 | 10                            |
| Vitamin E (µmol/l)                               | 18 | 7                             |

Table 2. Cutoff levels to determine blood level compliance

The disagreement in the classification of subjects from the PP and compliance population will be described qualitatively (e.g. not included in PP due to non-compliance reason, blood level suggest control non-compliance, etc.). McNemar's test will be used to compare inclusion in the PP and the compliance population. If significantly different, driven by product compliance reason, analyses will also be conducted in the blood level compliance population.

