4.1 Number of subjects

Total number of subjects to be enrolled: 200 (unequal allocation: 65/65/35/35 for Combination/Placebo/DHA only/Vitamin E only groups, respectively). With an estimated 10% attrition, approximately 180 subjects are expected to complete the study.

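### Re-analysis in the blood-level compliance set depends on McNemar's test, which cannot detect balanced disagreement with the PP set

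*SAP*

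**What the plan says.** SAP 6.5 gives the purpose of the blood levels: they "will be used to confirm the accuracy of capsule counts used in the determination of the PP population". After database lock, each subject is classed by the change in plasma DHA and α-tocopherol, with cut-offs and rules that depend on the arm. Three steps follow.

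- Description, always done: "The disagreement in the classification of subjects from the PP and compliance population will be described qualitatively".
- Test: "McNemar's test will be used to compare inclusion in the PP and the compliance population".
- Conditional re-analysis: "If significantly different, driven by product compliance reason, analyses will also be conducted in the blood level compliance population".

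The set compared with the blood-level set is PP, which SAP 6.2 builds from more than capsule counts. "The per protocol (PP) will include subjects who completed the study according to the protocol"; eligibility failures are removed; and "Data will be excluded if the subject has other significant protocol deviations or significant non-compliance with study product". Membership is settled at a blinded data review meeting.

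For the capsule count, SAP 6.2 divides capsules provided minus returned by expected capsules, with 80% as the threshold. Expected capsules are "defined as the duration of treatment (end of study medication- start of study medication +1) multiplied by three".

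**The concern.** Confirming capsule counts means asking whether two methods class the same people alike. McNemar's test asks something else: whether the two sets include the same proportion of subjects. Two methods can disagree on many individuals and still include equal proportions.

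The choice of comparator makes this worse. A subject can leave PP for an eligibility failure, non-completion or another deviation and still have adequate blood levels. That subject falls in the discordant cell opposite to a subject whom the capsule count wrongly passes, and the two cancel in the test. The gate can therefore stay closed in the case it was meant to catch.

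The second condition, that compliance drives the difference, does not help. It is an added requirement, so it cannot open a gate that the test has closed. No rule is given for judging it, and it is judged once treatment is known.

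At stake is the hepatic-fat estimate in subjects whose blood levels confirm intake.

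**Working it through.** **Inputs.** The test and gate are in SAP 6.5. SAP 8.0 sets two-sided 0.05. Neither document gives an expected number of discordant subjects, so there is no plan figure to reproduce and the counts below are assumed. The SAP does not say whether the test is exact or asymptotic, so both are shown.

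**Set-up.** Let b be the subjects in PP whose blood levels fail (capsule counts wrongly pass them). Let c be the subjects outside PP whose blood levels are adequate. This takes the blood-level set as drawn from all subjects, not nested within PP. SAP 6.5 supports that: it classes each subject, and its examples of disagreement include subjects left out of PP.

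**Formulas.**
- Exact: p = min(1, 2 × P(X ≤ min(b, c))), with X binomial(b + c, 0.5).
- Asymptotic: (b − c)² / (b + c), referred to chi-square with 1 df, no continuity correction.

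| b v c | Exact p | Asymptotic p | Gate |
|---|---|---|---|
| 20 v 20 | 1.00 | 1.00 | closed |
| 12 v 0 | 0.0005 | 0.0005 | open |
| 12 v 4 | 0.077 | 0.046 | depends on version |
| 12 v 5 | 0.14 | 0.090 | closed |
| 12 v 6 | 0.24 | 0.16 | closed |

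For 12 v 5, the asymptotic statistic is 7² / 17 = 2.88. The first row is 40 subjects classed differently, 20% of 200. Its p-value needs no assumption about size: whenever b = c, p = 1.00.

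**Range.** Smallest b that gives p < 0.05, by c:

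| c | 0 | 5 | 10 | 20 |
|---|---|---|---|---|
| Exact | 6 | 15 | 23 | 36 |
| Asymptotic | 4 | 14 | 21 | 35 |

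**Can c be above zero?** Protocol 4.1 says "With an estimated 10% attrition, approximately 180 subjects are expected to complete the study", so about 200 − 180 = 20 subjects would be outside PP for non-completion alone. Some may have blood levels: they are drawn at 3 months, and Protocol 8 seeks the final-visit laboratory tests at withdrawal. How many would pass the blood rule cannot be derived from the documents.

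**Capsule denominator.** A kit holds 13 × 42 + 21 = 567 capsules (Protocol 5.1.3). If the end of study medication means the last dose, a subject who takes every dose, stops on day 60 and returns 387 scores (567 − 387) / (60 × 3) = 180/180 = 100%. Against the planned 180 days the figure is 180/540 = 33%.

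**The case against.** The strongest reply is that the capsule-versus-blood question does not rest on this gate. Protocol 9.3.6 compares plasma DHA and α-tocopherol by treatment in completers with at least 80% intake, and applies Fisher's exact test to the proportions at least 80% compliant. SAP 8.3 models both plasma levels by arm at 3 and 6 months. The disagreement is also described qualitatively in every case. All of this stands, so a reader who inferred that a closed gate leaves capsule counts unchecked would be going too far. None of these steps, however, estimates hepatic fat in subjects whose blood levels confirm intake.

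Second, the discordant counts are invented. This also stands. One might infer from the 12 v 5 row that five of the roughly 20 expected non-completers would be enough to close the gate. That holds only if 12 subjects are wrongly passed and five non-completers meet the blood rule. SAP 6.5 does not say how to class a subject without a 6-month level, and treated subjects who stop early may fail the blood rule too, which would make them concordant exclusions. The algebra is firm; the scenario is illustrative.

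Third, the blood-level set is formed after randomization and unblinding, with unequal rules: the combination arm is excluded only if neither analyte rises enough, while each single-agent arm faces two conditions. That limits what the analysis can show, but is no reason to make it depend on an unsuitable test.

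On the denominator, one might infer that early stoppers enter PP with a perfect score. The documents do not support that in general: PP requires completion according to the protocol, excludes other significant deviations and passes through blinded review. The gap concerns subjects who stop capsules, still attend the 6-month visit and are not removed on those grounds. Nor can an effect on compliance Table 1.3 be sized, since SAP 12.0 gives only its title.

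**Conclusion.** The point holds and is minor. The rule in SAP 6.5 can suppress the blood-level re-analysis when disagreement is large, because the test sees imbalance and not disagreement. For balanced cells this is certain at any size. For partly offset cells it depends on counts that the documents do not give. The reasoning assumes that the blood-level set is not nested within PP. The loss is confined to one supportive analysis; the primary ITT/mITT result does not change.

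The denominator reduces to an undefined term in SAP 6.2. The 100% score follows only if the end of study medication is read as the last dose taken; if another date was meant, one sentence settles it.

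**What to change.** In SAP 6.5:

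- Remove McNemar's test as a condition for further analysis.
- Report, by arm, a cross-table of capsule-count compliance (at least 80%) against blood-level compliance, with the two discordant counts and percent agreement. Show subjects with missing levels separately. Using capsule-count compliance in place of PP keeps unrelated exclusions out of the comparison.
- Run the SAP 8.2 hepatic-fat model in the blood-level set in every case. Label it supportive, because its exclusions are post-randomization, unblinded and use different rules by arm.

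In SAP 6.2, define the end of study medication so that stopping capsules early while still attending the 6-month visit does not score 100%. One way is to count expected capsules to the actual end-of-treatment visit, or to planned day 180 for those who withdraw. A fixed 540 for everyone is not a good substitute, because it shifts the threshold with visit timing inside the allowed window. The 80% mark is 0.80 × 540 = 432 capsules. At day 173 that is 432/519 = 83.2% of doses due, so subjects between 80.0% and 83.2% would newly fail. At day 183 it is 432/549 = 78.7%, so subjects just under 80% would pass.

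The cost is SAP wording, one table and one extra model run, for a result that can only be supportive.

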# 7.0 Determination of Sample Size and Randomization

As indicated in section 9.3.7 of the study protocol, with 60 subjects per arm for the combination (DHA EE + vitamin E) and PBO groups, there is 80% power to detect a 3.64% absolute reduction in liver fat assuming a standard deviation of 7% and a two-sided 0.05 significance level with a two-sample t-test (G\*power 3.1.9.2). To estimate the secondary endpoints of the PBO compared to the components (DHA EE, vitamin E) with a given precision of ±3% of liver fat, a total of 30 subjects per arm are needed for the

DHA EE and the vitamin E groups. Accounting for an expected 10% attrition, the resulting required sample size was 200 subjects.

Subjects will be randomly assigned to one of four treatment arms following an unequal allocation of 65/65/35/35 for combination (DHA EE + vitamin E), PBO, DHA EE, and vitamin E, respectively. A computer generated randomization scheme (i.e. interactive web based response system [IWRS]) will be used to assignment stratified by Type II diabetes.

# 8.0 Statistical Methods

Unadjusted descriptive statistics will be provided per measured time point. Continuous variables will be summarized with mean, standard deviation, median, and range. Categorical variables will be summarized with counts and percentages. All tests of significance are two-sided and considered significant at the 0.05 level. All confidence intervals presented will be 95% and two-sided. SAS version 9.4 or higher will be used for statistical analyses unless otherwise stated.

# 8.1 Demographic and Baseline Variables

Subject demographics of randomized subjects will include age, sex, diabetes strata, ethnicity, and race collected at the first screening visit overall and by treatment assignment. Summary demographics will be provided by treatment group for the study populations defined in section 6.0.

The following describes the time point used as the baseline measures for the outcome variables:

- Baseline hepatic fat fraction[%] as measured by MRI-PDFF is collected at the second screening visit (Visit 1)
- Baseline anthropometric measures are collected at the first screening visit (Visit 0)
- Baseline HbA1c, fasted insulin and fasting glucose are collected at the first screening visit (Visit 0)
- Baseline liver enzymes (AST, ALT, ALK-P) and bilirubin are collected at the first and second screening visits with the allowance for a 3rd unscheduled pre-treatment visit. The measurement closest to the date of randomization will serve as the baseline measure.
- Baseline Fibrosis-4 score is collected at the first screening visit (Visit 0)
- Baseline plasma vitamin E and DHA concentrations are collected at the second screening visit (Visit 1)
- The baseline lipid panel profile is collected at the second screening visit (Visit 1)
- The baseline responses to the short-form health survey (SF-36) is collected at the randomization visit (Visit 2)
- The baseline food frequency questionnaire (FFQ) for the LC-PUFA is collected at the randomization visit (Visit 2)
- Baseline inflammatory markers are collected at the second screening visit (Visit 1)
- Baseline AUDIT questionnaire total score collected at the first screening visit (Visit 0)

#### 8.2 Primary Endpoint Analysis

The 6-month hepatic fat fraction [%] will be evaluated with a linear mixed analysis of covariance (ANCOVA) model. Baseline hepatic fat fraction [%], intervention group, and baseline diabetes status will be included as fixed effects. Study site will be included as a random effect. The residuals of the model will be analyzed visually (QQ-plots, residual plots) to verify model assumptions (normality, constant variance, homogeneity) are met. If necessary, a variance stabilizing transformation (i.e. log) may be considered. The impact of the random effect will be evaluated with the likelihood ratio test and may be removed if not significantly adding to the model. The model derived pairwise comparison between the combination (DHA EE + vitamin E) and PBO will be estimated using least squares means and tested for significance with a t-test. Since the primary outcome is the pre-specified comparison of DHA EE + vitamin E compared to PBO at 6-month, no adjustment for multiple comparisons is planned.

Note that the estimate of the treatment effect is computationally identical to an analysis that utilizes the change score (6-month vs. baseline) as the response variable adjusted for baseline, intervention group, and baseline diabetes status as fixed effects and site as a random effect. However, the 6-month response variable was selected to allow for easier variance stabilizing transformations if necessary.

#### 8.3 Secondary Endpoint Analyses

- The linear mixed model described in section 8.2 for the 6-month hepatic fact fraction [%] will also be used to estimate the difference between DHA EE and PBO, and vitamin E and PBO. The respective model derived pairwise comparisons will be estimated along with a 95% confidence interval. A Dunnett correction for multiple comparisons will be used.
- The between group differences in the anthropometric measures, liver enzymes, FIB-4 score, plasma Vitamin E (α-tocopherol), plasma DHA, and lipid panel will be estimated at 3 and 6 months with a linear mixed ANCOVA model. The respective follow-up measure, at each of 3 and 6 months, will be the response vector. Fixed effects will include the respective baseline anthropometric measure, intervention group, diabetes stratification, time point, and intervention group by time point interaction. Clinic site will be the random effect. Model derived pairwise comparisons of DHA EE + vitamin E vs. PBO, vitamin E vs. PBO, and DHA EE vs. PBO at 3 and 6 months will be estimated along with 95% confidence intervals. The Holm method will be used to adjust for the 6 planned comparisons (i.e. the LSMESTIMATE statement in SAS). Note, the purpose of the model is to estimate the effect at 3 and 6 months, adjusted for baseline, and not evaluate the trend which would require a joint test of intervention group and the intervention group by time interaction.
- At 6-month, the differences of each intervention group to PBO in insulin resistance measures, SF-36 domains, and inflammatory markers will be estimated with a linear mixed ANCOVA model. The respective baseline measure, intervention group, and baseline diabetes status will be included as fixed effects. Study site will be included as a random effect. Pairwise comparisons of DHA EE + vitamin E vs. PBO, vitamin E vs. PBO, and DHA EE vs. PBO will be estimated along with 95% confidence intervals. A Dunnett correction for multiple comparisons will be used.

The differences between intervention groups (DHA EE + vitamin E vs. PBO, vitamin E vs. PBO, DHA EE vs. PBO) in dietary intake of LC-PUFA, specifically DHA and EPA, will be assessed over time with a linear mixed model following an ANOVA approach. Fixed effects will include the intervention group, categorical time point (baseline, 1 month, 3 months, 6 months), and intervention group by time point interaction. A random intercept and a random time effect for subject nested within site will be included. For the random time effect, the covariance structure (e.g compound symmetry, unstructured) will be selected such that the AICC (corrected Akaike information criterion) is reduced. If a significant interaction effect is indicated, an interaction plot will be produced and the relevant pairwise comparisons between intervention groups and PBO at each time point (i.e. DHA EE + vitamin E vs. PBO, vitamin E vs. PBO, DHA EE vs. PBO) will be estimated along with a 95% confidence interval (CI) at each modeled time point. The Benjamini-Hochberg (false discovery rate) adjustment will be used for the 12 planned comparisons. Additionally, the model derived change from baseline to each follow-up time point will be estimated along with a 95% confidence interval.

For each model, the residuals of the model will be analyzed visually (QQ-plots, residual plots) to verify model assumptions (normality, constant variance, and homogeneity) are met. If necessary, a variance stabilizing transformation may be considered. The impact of the random effect(s) will be evaluated with the likelihood ratio test and may be removed if not significantly adding to the model.

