# 8.5 Post hoc analysis

If a positive intervention effect is indicated based on the primary outcome, the 6-month biomarker levels (i.e. ELF and Pro-C3) will be evaluated with a linear mixed analysis of covariance (ANCOVA) model. Baseline biomarker level, intervention group, and baseline diabetes status will be included as fixed effects. Study site will be included as a random effect. Pairwise comparisons of the combination (DHA EE + vitamin E) vs PBO, vitamin E vs. PBO, and DHA EE vs. PBO will be estimated along with 95% confidence intervals. A Dunnet correction for multiple comparisons will be used.

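### SAP 8.3 and 8.5 name a Dunnett correction without saying which version; step-down Dunnett would give the adjusted p-values more power at the same family-wise error

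*SAP*

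**What the plan says.** In SAP 8.3 the first bullet (DHA EE vs placebo and vitamin E vs placebo on 6-month liver fat) and the third bullet (three contrasts with placebo for insulin resistance, SF-36 domains and inflammatory markers) both end: "A Dunnett correction for multiple comparisons will be used". SAP 8.5 says the same for ELF and Pro-C3: "A Dunnet correction for multiple comparisons will be used". The footnote to the first example table in SAP 12.1 attributes the adjusted p-value to Dunnett, again without a version.

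The second bullet of SAP 8.3, for outcomes at 3 and 6 months, uses a step-down procedure: "The Holm method will be used to adjust for the 6 planned comparisons (i.e. the LSMESTIMATE statement in SAS").

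SAP 8.0 sets the general rules: "All tests of significance are two-sided and considered significant at the 0.05 level", and "All confidence intervals presented will be 95% and two-sided". It does not say whether intervals are adjusted for multiplicity. SAP 8.2 leaves the combination-versus-placebo liver-fat contrast, the primary test, unadjusted.

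**The concern.** Single-step Dunnett compares every contrast with the critical value for the whole family, even after stronger contrasts have been rejected. Step-down Dunnett tests the strongest contrast against that same value, then tests the rest against the smaller value for the contrasts that remain. By the closed-testing principle it still controls family-wise error strongly. Its adjusted p-value equals the single-step one for the strongest contrast and is never larger for the others. So for adjusted p-values, single-step gives up power and gains no error control.

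The contrasts that lose most are the single-agent ones. They rest on the smallest arms (35 randomized each), and on liver fat they are the first two secondary objectives. The SAP already accepts stepping down in the second bullet of 8.3.

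**Working it through.** **Inputs.** SAP 7.0 takes 60 evaluable subjects in each of the combination and placebo arms. Its planning statement is: "there is 80% power to detect a 3.64% absolute reduction in liver fat assuming a standard deviation of 7" (percentage points). The test behind it is a two-sample t-test at two-sided 0.05. For the single agents, "a total of 30 subjects per arm are needed". Allocation is 65/65/35/35 with 10% attrition. *Assumption:* the documents give no effect for the single agents or for the other outcomes, so 3.64/7 = 0.52 SD is carried over to every active arm and then varied. Baseline adjustment and site variance are ignored.

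**The plan's own figure.** With 60 per arm, SE = 7√(2/60) = 1.278 and 3.64/1.278 = 2.85. Exact noncentral-t power is 80.6% at 60 per arm and just under 80% at 59. The stated 80% with 60 per arm reproduces, and 180/0.9 = 200.

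**Critical values.** These were simulated with a shared placebo arm, evaluable 60/60/30/30 and 174 degrees of freedom (180 less four arms and two covariates). Correlations between contrasts are √[n_i/(n_i+n_0) × n_j/(n_j+n_0)]: 0.33 between the single agents and 0.41 between the combination and a single agent.
- Three contrasts: 2.387
- Two contrasts: about 2.24
- One contrast: 1.974

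**Check by formula, single-agent contrast.** SE = 7√(1/60 + 1/30) = 1.565 and 3.64/1.565 = 2.326. Single-step power ≈ Φ(2.326 − c):
- Family of two: Φ(2.326 − 2.245) = 53.2%
- Family of three: Φ(2.326 − 2.387) = 47.6%
- Unadjusted: Φ(2.326 − 1.974) = 63.8%

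The simulation gives 53.3%, 47.7% and 63.8%.

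**Single-step against step-down.** Step-down was run as the closed test over all subsets of contrasts. Effects are in points of liver fat with SD 7.

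| Family | True effects | Contrast | Single-step | Step-down | Gain (points) |
|---|---|---|---|---|---|
| Two single agents | 3.64 / 3.64 | each | 53.3% | 58.5% | 5.3 (before rounding) |
| Two single agents | 1.82 / 1.82 | each | – | – | 1.4 |
| Two single agents | 3.64 / 0 | the active one | – | – | 0.2 |
| Three | all 3.64 | single agent | 47.7% | 56.4% | 8.6 (before rounding) |
| Three | all 3.64 | combination | 67.7% | 72.2% | 4.5 |
| Three | combination 3.64, single agents 1.82 | single agent | 11.3% | 15.2% | 3.9 |
| Three | combination 3.64, single agents 0 | combination | 67.8% | 67.9% | 0.1 |

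With expected completers of 58.5/58.5/31.5/31.5 (0.9 times the allocation), the first row becomes 54.6% to 59.8% and the single-agent row with all effects 3.64 becomes 49.0% to 57.5%.

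**Upper limit.** If every other contrast is almost sure to be rejected, the last one is tested at 1.974. At 3.64 points that is 63.8 − 53.3 = 10.5 points (two contrasts) or 63.8 − 47.7 = 16.1 points (three). Over all effect sizes the limits are about 10.7 and 16.2. The probability of at least one rejection does not change (72.6% and 82.7% at equal effects of 3.64).

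**Family-wise error.** Under the global null it is 5.0% for both methods. If only the combination works in a three-contrast family, it is 3.5% single-step and 4.5% step-down. No partial null examined exceeded 4.5%.

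**Interval widths, single agent vs placebo.** Unadjusted: 1.974 × 1.565 = ±3.09. Dunnett-adjusted: 2.245 × 1.565 = ±3.51 (two contrasts) or 2.387 × 1.565 = ±3.74 (three). The ±3 precision target in SAP 7.0 fits unadjusted intervals only.

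**The case against.** The strongest reply is that the plan treats the single-agent contrasts as estimation. Both documents size those arms for ±3 points of precision with no power target, and protocol 1.4 includes them for insight and safety data. Single-step Dunnett also yields simultaneous confidence intervals that agree with its p-values, which step-down does not do simply. Every extra rejection is a contrast whose single-step simultaneous interval still contains zero. The effect is also limited: the example table already prints the estimate, interval and raw p-value beside the adjusted p-value, and the biomarkers in SAP 8.5 are tested only after a positive primary result.

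Much of this stands, and it is why the point is an improvement rather than a fault. The interval argument is weak here. The SAP never calls its intervals simultaneous, its precision target matches unadjusted ones, and it already pairs 95% intervals with step-down Holm p-values. Because the SAP does ask for adjusted p-values, the choice of procedure matters even where estimation comes first.

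A reader might infer that the SAP prescribes single-step Dunnett. It does not; that is only the default reading of an unqualified term. A reader might also take a gain of 10 points as general. In a three-contrast family a gain of about 10 needs assumed effects such as 0.70 SD (combination) and 0.60 SD (single agents), which are not in the documents. In the liver-fat pair it is approached only when the other agent is almost certain to be rejected.

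**Conclusion.** The point holds as an efficiency improvement for adjusted p-values of secondary and post hoc contrasts. At an assumed 0.52 SD in every active arm, step-down Dunnett adds about 5 points of power per single-agent contrast in the liver-fat pair and 8 to 9 points in three-contrast families, with family-wise error still at 5%. The gain falls to about 0 to 4 points when effects are smaller or other arms are null, and rises when the other contrasts are strong. These sizes rest on the carried-over effect, normal outcomes with a common SD, and the family sizes used.

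The documents do not support reading this as an invalid analysis or as a threat to the primary conclusion. Either version of Dunnett is valid, and the primary contrast is tested without adjustment.

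**What to change.** - In SAP 8.3 (first and third bullets) and SAP 8.5, replace the Dunnett sentence with wording such as: *Step-down Dunnett-adjusted p-values will be reported, based on the joint distribution of the contrasts with placebo named here.*
- State the family in each place: two single-agent contrasts for liver fat, because the combination contrast is the unadjusted primary; three contrasts elsewhere. The generic example table has an adjusted p-value row across all three active columns, so it should say that this row does not apply to the combination for liver fat.
- Change the Dunnett footnote in SAP 12.1 to match.
- Keep the 95% intervals and label them unadjusted.

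The cost is a few lines of SAP text and a small programming change, with no extra patients or data. The downside is that the step-down p-values have no simple matching simultaneous intervals, so an adjusted p-value and its interval can disagree. That is already so for the Holm-adjusted outcomes. If matching simultaneous intervals are wanted instead, the SAP should say single-step and give that reason.
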